Sample. As shown in the consort diagram in Figure S1, of the 241 adults who filled out our eligibility questionnaire online, 38 were not eligible, 15 gave up as they had trouble downloading the app, 4 did not meet the age requirement, 4 indicating participating in a walking intervention would be a potential health risk, and 3 could not participate due to travel. One hundred and forty-three potential participants who were eligible did not respond when we notified them that they were eligible. Recruitment took place from October 2018 to March 2019, with primary data collection completed in February 2019, and follow-up data collection completed in March 2019. Those who were

physically active (i.e., who had 7,000 - 10,000 daily steps or above everyday) were not included after the one-week baseline. A total of 60 adults were recruited and randomly assigned to either the control condition ($n = 30$) or the treatment condition ($n = 30$). They completed the study in one of three subgroups, with 20 participants randomly assigned into two groups (10 in treatment group, and 10 in control group) for each subgroup.

Measures

Covariates. Age, gender, education, race, and self-reported health were used as covariates in the analyses because of their expected relationship with the outcome measures. For physical health, the participants were asked “in general would you say your health is?” The response options ranged from 1 (poor) to 5 (excellent) with a higher score indicating better physical health.

The outcome measures were administered at the pretest, posttest and follow up using self-report questionnaires given before and at the completion of week 4 of the pilot study and at the 1 month follow up through an online platforms-Qualtrics.

Daily step counts. Participants' daily steps were recorded by using the WeRun function in WeChat by the end of each day during the 4-week intervention period and at the 1 month follow up. Mean daily steps for pretest week, post-test week and one month follow up week were calculated as the mean number of steps across the 7 days in that week of the study.

Percentage change in mean weekly steps at posttest was calculated as the difference between the mean weekly steps at posttest and pretest divided by the mean weekly steps at pretest. The percentage change in mean weekly steps at the one month

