Statistical analyses of survey measures were done using SPSS. Descriptive information and correlations were computed for all study variables. Changes in daily steps, social engagement and exercise self-efficacy from the pretest to 4 weeks were examined. Repeated measures ANCOVA was used to test for effects of the treatment on mean daily step counts over the intervention period, exercise self-efficacy, and social engagement and to compare treatment and control groups at pretest, posttest, and follow-up using a two condition by three occasions design. All post hoc analyses were performed using Bonferroni corrections controlling the covariates. We conducted a sensitivity analysis without the covariates and the results were the same.

Conditional process modeling was applied using PROCESS in SPSS to test the predicted mediation model. Mediation analyses was based on 1000 bootstrapped samples using Hayes’ PROCESS Macro v3.3 (Hayes & Preacher, 2014), allowing for formal tests of the total, direct, and indirect effects of intervention on percentage of change of mean weekly steps from pre-test to post test. The predictor variable was condition, the mediator variable was change in social engagement, and the outcome was percent change in mean weekly steps from pre-test to post test.

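### The mediation model's two randomised contrasts use change scores without pretest adjustment and lose some precision; its indirect effect should be worded as exploratory

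*Combined protocol and SAP*

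**What the plan says.** The Data Analysis Plan takes condition as predictor and states that "the mediator variable was change in social engagement, and the outcome was percent change in mean weekly steps from pre-test to post test". It describes the model as "allowing for formal tests of the total, direct, and indirect effects of intervention on percentage of change of mean weekly steps", and says "Mediation analyses was based on 1000 bootstrapped samples". Under Measures, Daily step counts, "Percentage change in mean weekly steps at posttest was calculated as the difference between the mean weekly steps at posttest and pretest", divided by the pretest value. Under Measures, Covariates, "Age, gender, education, race, and self-reported health were used as covariates in the analyses". Neither pretest LSNS nor pretest steps is on that list, although the Design section has both collected before assignment. The plan does not say whether the listed covariates were entered in the mediation model.

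A separate analysis also bears on the condition effects: "Repeated measures ANCOVA was used to test for effects of the treatment on mean daily step counts over the intervention period", and the same sentence extends it to exercise self-efficacy and social engagement.

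Objective (b) asks whether engagement mediates the effect, and equates a significant mediator with a mechanism by which behaviour changes. The mediation model is the only analysis described for that objective. The plan states no assumption about common causes of engagement and steps.

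**The concern.** Two parts of the model need to be kept apart.

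The first part is what randomisation protects: condition to engagement, and the total effect of condition on steps. With a change score and no pretest term, part of the pretest noise stays in the residual. A trial of 60 people can ill afford that loss when the pretests are already on file.

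The second part is the path from engagement to steps. Nobody was assigned a level of engagement, and both changes run from pretest to posttest. The indirect effect is the product of a randomised path and this one, so its causal reading needs two things that the trial cannot verify: no unmeasured common cause of engagement and steps, and engagement changing before steps. The same applies to the direct effect, which conditions on the mediator. What is at stake is how firmly objective (b) can be answered.

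**Working it through.** **Inputs from the document.** 60 randomised, 30 per arm (Sample); mediator, outcome and 1000 resamples (Data Analysis Plan); covariates and percent-change definition (Measures).

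**Inputs assumed, because the document gives none.** Pre-post correlation r from 0.5 to 0.9; CV of steps 0.5; lognormal steps; a true increase of 25% in steps and of 0.6 SD in engagement. The simulations contain no demographic covariates.

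**The plan's own figure.** The only design figure is 56 participants under Eligibility. It is not tied to the mediation analysis, and this point does not rest on it.

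**Step 1: engagement contrast.** With equal SD s at both occasions, the residual variance is 2s²(1−r) for a change score and s²(1−r²) with pretest adjustment. The ratio is 2(1−r)/[(1−r)(1+r)] = 2/(1+r). The adjusted analysis that would match the planned 60 people needs 60(1+r)/2 people. Power is for a 0.6 SD difference.

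| r | Variance ratio | Equivalent N | Power, change score | Power, pretest-adjusted |
|---|---|---|---|---|
| 0.5 | 2/1.5 = 1.33 | 45 | 63% | 75% |
| 0.7 | 2/1.7 = 1.18 | 51 | 84% | 89% |
| 0.9 | 2/1.9 = 1.05 | 57 | about 100% | about 100% |

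**Step 2: total effect on percent change in steps.** The formula in Step 1 does not apply exactly to a ratio, so this was simulated.

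| r | Percent change, as planned | Percent change + pretest steps | Log posttest + log pretest steps |
|---|---|---|---|
| 0.5 | about 40% | 48-49% | 54% |
| 0.7 | 62% | 66-68% | 70% |
| 0.9 | 98% | almost no gain | 98-99% |

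A separate run of 4,000 replicates gave 47% and 67% for the middle column at r 0.5 and 0.7. That agrees within simulation error: at 48%, one standard error is √(0.48 × 0.52/4000) = 0.8 points. Only the step from the second column to the third is due to pretest adjustment. The step to the last column comes from the log scale, which also changes the estimand to a ratio of geometric means.

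**Step 3: type I error.** With no effect of condition, rejection rates were 4.5-5.3% for the planned model and 4.4-5.4% for the adjusted log model. The loss is of precision, not of validity.

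**Step 4: baseline exclusion.** The Sample section says that those "physically active (i.e., who had 7,000 - 10,000 daily steps or above everyday) were not included after the one-week baseline". Narrowing the pretest range shrinks the gain. For the log model at slope 0.5, power is 39% against 54% with no exclusion (15 points). It is 43% against 54% if the top 20% of pretest steps are cut (11 points), and 45% against 53% if the top 40% are cut (8 points).

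**Step 5: engagement-to-steps path, true effect zero.** False-positive rates at r 0.5/0.7/0.9; rho is the assumed correlation between the two pretests, or between the two traits:
- Each posttest depends on its own pretest, rho 0.5: planned 15/9/5%, with both pretests about 5%. At rho 0.3 the planned model gives 8/7/5%.
- The pretests share only a stable trait, rho 0.5: planned about 5%, with pretests 10/8/5.5%.
- The posttests share a fluctuation (residual correlation 0.3): planned 38-86%, with pretests 62-64%, over r from 0.5 to 0.9.

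If steps drive engagement, a false indirect effect appears in 13-34% of trials with the planned model and 20-37% with pretests. The document gives nothing with which to choose among these structures.

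**The case against.** The strongest reply is that the precision point is peripheral. The condition effects belong to objective (a), where the repeated measures ANCOVA tests them on steps and on social engagement. A sharper total effect inside the mediation model changes little for objective (b). This stands as a limit on weight. However, the plan presents the total effect as a formal test, and the improvement uses data already held.

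A second reply is that the listed covariates, if they were entered, may already absorb part of the pretest variation, so the gain could be smaller than simulated. That also stands.

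A third is that a non-randomised mediator is a familiar limitation of trial mediation analyses, and that the plan describes itself as an exploratory pilot and reports no mediation result. This is why the remedy is wording and not a different analysis.

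A reader might go further in four ways that the documents do not support:
- That change scores bias the randomised comparison. They do not; type I error stays near 5%.
- That the whole rise from about 40% to 54% is due to pretest adjustment. At r 0.5 about half of it is a change of scale.
- That adding pretests repairs the indirect effect. Step 5 shows that it helps under one structure, harms under another and fails under a third.
- That the indirect effect can never be more than an association. That is too absolute: a causal reading is possible under stated assumptions, and the plan only sets out to explore the question.

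**Conclusion.** The point holds as a cheap improvement in precision together with a caution on wording. Neither randomised contrast is invalid. Without pretest adjustment, the engagement contrast has 1.05 to 1.33 times the variance it needs for r from 0.9 down to 0.5. For percent change in steps, the avoidable loss of power is about 8-9 points at r 0.5 (40% against 48-49%), 4-6 points at r 0.7 (62% against 66-68%) and almost nothing at r 0.9. These sizes rest on assumed r, CV and effect, and the baseline exclusion reduces them.

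For the indirect effect, the limit is the missing randomisation of engagement and the shared interval. No choice between the planned model and a pretest-adjusted one removes it.

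**What to change.** 1. Add pretest LSNS to the condition-to-engagement contrast, and pretest steps (or log pretest steps) to the percent-change contrast, each with the covariates already listed. Keep percent change as the outcome. Report the planned unadjusted result beside it.
2. A model for log posttest steps is optional. If used, state that it estimates a ratio of geometric means and that part of its extra power comes from the scale.
3. Leave the repeated measures ANCOVA in place; these additions do not replace it.
4. Describe a significant indirect effect as exploratory and consistent with mediation, provided that no unmeasured factor drives both engagement and steps and that engagement changes first. Do not present it as a demonstrated mechanism. A second indirect-effect model is optional; if reported, say what each model assumes and do not claim that adjustment restores 5% error.

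The cost is one further run on existing data and some rewording. The Sample section shows that data collection is complete, so the additions are post hoc and must be labelled so. The gain cannot be known in advance, because r and CV are not given.
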